19.2.2 Secondary endpoint analysis

Incidence and timing of severe complications of cirrhosis from the date of diagnosis of cirrhosis (in clinic, date of clinic visit or blood sample) will be analysed using Cox regression analysis, adjusting for the minimisation factors (see section 12.2), and will be used to compare the differences between the control and ELF arm. Overall survival curves will be calculated using the Kaplan-Meier method, hazard ratios and corresponding 95% confidence intervals will be presented.

Timing to diagnosis of cirrhosis will be calculated from date of randomisation to the date the patient is diagnosed as having cirrhosis (in clinic) either by, in the ELF arm, having an ELF score ≥ 9.5 or in the control arm, via standard methods. Cox regression analysis, adjusting for the minimisation factors (see section 12.2), will be used to compare the differences between the survival curves, which will be calculated using the Kaplan-Meier method. Hazard ratios and corresponding 95% confidence intervals will be presented.

Detection and timing of complications of cirrhosis will be calculated from the date of diagnosis of cirrhosis, to the detection of the first event. An 'event' in this instance encompasses small and large varices, treatable HCC and inoperable HCC. Cox regression analysis, adjusting for the minimisation factors, will be used to compare the differences between the survival curves. Overall survival curves will be calculated using the Kaplan-Meier method, hazard ratios and corresponding 95% confidence intervals will be presented.

Details of all causes of mortality will be collected and documented, specifically including the number of deaths and whether or not they are suspected to be related to any treatments/trial procedures. All liver-related mortalities will be summarised separately.

Details of the economic evaluation of the ELF test are given in Section 16.

For Quality of Life (QoL), we will look at the difference in expected quality-adjusted survival to final follow-up using the Cox proportional hazards model. We will examine the impact of missing data using a Multiple Imputation method.

The proportion of non-randomised patients (where ELF < 8.4 indicating minimal/mild liver fibrosis) who go on to develop cirrhosis during the follow-up period will be summarised in order to assess false-negative rates (see section 6.3).

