17.2 SECONDARY ENDPOINTS

- Time from diagnosis of cirrhosis (by ELF or clinical means) to incidence of first severe complication

* Milan criteria: One lesion less than 5cm, up to 3 lesions smaller than 3cm, no extrahepatic manifestations, no vascular invasion.

- Time from randomisation to diagnosis of cirrhosis by ELF or clinical means (to allow instigation of prophylaxis and screening)
- Process outcomes, namely:
 - treatment with beta-blockers/band ligation (BB/BL) of varices
 - use of endoscopy and ultrasound/AFP tests
 - treatment to normalise LFTs in patients with Hepatitis B and Hepatitis C.
- Detection and timing of complications following cirrhosis, including:
 - Detection of small varices
 - Detection of large varices
 - Incidence of treatable hepatocellular cancer (HCC)
- All causes of mortality
- Specific liver-related morbidity
- Economic evaluation of the ELF test in the early detection of cirrhosis and as such in the initiation of measures to reduce the incidence of severe complications following cirrhosis.
- Quality of Life (QoL)
- Proportion of non-randomised patients (ELF < 8.4) who go on to develop cirrhosis (diagnosed by clinical means) within the follow-up period.

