9.49 to develop cirrhosis during the 24 months of recruitment and 36 months of follow-up, which when added to the 185 patients who present with cirrhosis in this arm through having an ELF >9.49 gives a total of 216 patients developing cirrhosis in the ELF arm. In the control arm we expect 185 patients to have an ELF >9.49 and we expect approximately 46 of these to develop severe complications after 24 months of recruitment and 36 months of follow-up and therefore be diagnosed as cirrhotic at that point. We expect a further one third of these 185 patients to be diagnosed as cirrhotic on clinical grounds which adds another 62 patients. In addition we estimate that approximately 10% of the 315 patients with an ELF score between 8.4 and 9.49 will progress to cirrhosis on clinical grounds. This gives a total of 139 patients developing cirrhosis in the control arm. Therefore we are expecting approximately 31/216 patients encountering severe complications in the ELF arm subsequent to development of cirrhosis compared with approximately 52/139 in the control arm, after 24 months of recruitment and 36 months of follow-up. With a type I error rate of 5% we would have >99% power to detect this difference in this secondary endpoint.

The trial as its original size was thus well powered (at least 90% for the primary endpoint from randomisation with an additional 5 years of follow-up) to show that this ELF monitoring policy will be of real clinical benefit.

Following the recommendation by the funding body to close the trial to recruitment, it is anticipated that by the time the resulting protocol amendment is approved and implemented, approximately 700 patients will have been randomised. Based on this, and with follow-up continuing until July 2014, the trial will have adequate statistical power to report on changes in the process of the care which are critical to the prevention of gastro intestinal haemorrhage and Hepatocellular Carcinoma (HCC) in patients with chronic liver disease who are monitored using the ELF test.

The first process of care would be the use of beta-blockers/band ligation (BB/BL) of varices to prevent haemorrhage. The ELUCIDATE trial will not report the major liver events and survival within the period of the Programme. However, recruitment as planned will be sufficient for these analyses if the patients are followed for a further five years and additional funding is being sought to complete this work.

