19.2 STATISTICAL ANALYSIS POPULATIONS

All analyses will be conducted on the intention-to-treat (ITT) population and carried out at a 2-sided 5% level of significance. The ITT population is defined as all patients randomised to treatment regardless of non-compliance, loss to follow-up, or death.

The secondary endpoint analysis, incidence of cirrhosis in non-randomised patients, will be conducted on follow-up data from those patients who registered and consented to the trial, but who were not randomised due to having an ELF score of < 8.4 (see section 6.3).

Attempts will be made to retrieve missing data via a thorough data cleaning process.

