19.2.1 Primary endpoint analysis

Incidence and timing of severe complications of cirrhosis will be calculated from the date of randomisation to the occurrence of the first event (severe complication). Cirrhosis is diagnosed either by, having an ELF score ≥ 9.5 in the ELF arm or in the control arm, via standard methods. An 'event' encompasses variceal haemorrhages, spontaneous bacterial peritonitis, unresectable hepatocellular cancer, encephalopathy (grade 3 or 4) and liver

related mortality. Cox regression analysis, adjusting for the minimisation factors (see section 12.2), will be used to compare the differences between the control and ELF arm. Overall survival curves will be calculated using the Kaplan-Meier method, hazard ratios and corresponding 95% confidence intervals will be presented.

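### The endpoint timed from diagnosis of cirrhosis is not a randomised comparison: it can favour ELF when ELF prevents nothing, and its >99% power owes much to unequal denominators

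*Protocol*

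**What the plan says.** Protocol section 17.2 lists as a secondary endpoint "Time from diagnosis of cirrhosis (by ELF or clinical means) to incidence of first severe complication". Section 19.2.2 analyses "Incidence and timing of severe complications of cirrhosis from the date of diagnosis of cirrhosis" by Cox regression adjusted for the minimisation factors, with Kaplan-Meier curves, hazard ratios and 95% confidence intervals, to compare the arms. A later paragraph of 19.2.2 uses the same origin for varices and HCC: "Detection and timing of complications of cirrhosis will be calculated from the date of diagnosis of cirrhosis".

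The diagnostic rule depends on the arm. Section 19.2.1 states: "Cirrhosis is diagnosed either by, having an ELF score ≥ 9.5 in the ELF arm or in the control arm, via standard methods". Section 12.3 adds that the ELF arm is also screened by standard clinical means, and section 12.4 gives the control arm clinical means only.

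Section 18.1 powers the endpoint for 1000 patients. It expects "approximately 31/216 patients encountering severe complications in the ELF arm subsequent to development of cirrhosis compared with approximately 52/139 in the control arm" and concludes: "With a type I error rate of 5% we would have >99% power to detect this difference in this secondary endpoint". Among the 139 control patients it counts about 46 with ELF >9.49 who develop a severe complication and will "therefore be diagnosed as cirrhotic at that point".

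Section 19.2 says that all analyses use the intention-to-treat population of all randomised patients and are "carried out at a 2-sided 5% level of significance".

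**The concern.** Randomisation makes the arms comparable at randomisation. It does not make those later diagnosed in one arm comparable with those later diagnosed in the other when the test under study is itself the diagnostic rule in one arm only.

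- **Selection.** Section 18.1 assumes the same 185 patients with ELF >9.49 in each arm. In the ELF arm all 185 enter the comparison. In the control arm about 46 + 62 = 108 enter, and about 185 − 108 = 77 event-free patients never do.
- **Time origin.** For those 185 patients the ELF-arm clock starts at randomisation. The control clock starts at clinical diagnosis, which for about 46 patients is the complication itself. Their time to event is zero.
- **Population.** An analysis of diagnosed patients only cannot be the intention-to-treat analysis that section 19.2 promises for every comparison.

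At stake is a hazard ratio and p-value that could be read as evidence that ELF monitoring prevents severe complications when the design gives no such evidence. The protocol attaches no caution to the result.

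**Working it through.** **Inputs (section 18.1 unless stated).** 500 patients per arm, 185 of them with ELF >9.49; 52 control events; 31 ELF-arm events after a 40% reduction; 216 and 139 diagnosed; two-sided 5% (section 19.2).

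**1. The denominators.** ELF arm: 185 + 0.10 × 315 = 216.5. Control arm: 46 + 62 + 31.5 = 139.5. Both match the stated 216 and 139.

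**2. The stated power.** Power = Φ[(|p₁ − p₂| − 1.96·SE₀)/SE₁], with SE₀ pooled and SE₁ unpooled. Here p₁ = 31/216 = 0.1435, p₂ = 52/139 = 0.3741, difference 0.2306, SE₀ = 0.0460, SE₁ = 0.0475. Power = Φ(2.96) = 99.8%. The >99% is reproduced.

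**3. Where it comes from.** The planned risk ratio factorises:

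(31/216)/(52/139) = (31/52) × (139/216) = 0.596 × 0.644 = 0.384.

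Only 0.596 is the assumed effect of ELF. The factor 0.644 is the ratio of denominators. On randomised denominators, 31/500 v 52/500 gives (0.0420 − 1.96 × 0.01745)/0.01740 = 0.45, a power of 67%. This is close to the 70% that section 18.1 states for the primary endpoint at 30 months.

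**4. No effect of ELF.** Set the ELF-arm events to 52 and keep the protocol's denominators.

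- 52/216 = 24.1% v 52/139 = 37.4%, risk ratio 0.644.
- z = 0.1334/0.0495 = 2.69, p = 0.007 (Fisher p = 0.009).
- Rejection probability = Φ[(0.1334 − 1.96 × 0.0495)/0.0503] = Φ(0.72) = 76.5%, against a nominal 5%.
- The proportions become equal only at 52 × 216/139 = 81 ELF-arm events, about 55% more complications than control.

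**5. Does adjustment help?** Baseline ELF band is a minimisation factor (section 12.2). Within ELF ≥9.5 and with no effect, the counts are 46/185 = 24.9% v 46/108 = 42.6%, z = 0.1773/0.0562 = 3.15, p = 0.002. Conditioning on ELF band leaves the problem in place.

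**6. The planned model.** Section 19.2.2 plans Cox regression, so proportions are not enough. Null trials were simulated (1,500 per setting, unadjusted Cox from diagnosis). From the protocol: 22% events at 36 months in patients with ELF >9.49, 10% of the others progressing, 24 months of accrual and 36 months of follow-up. Assumed: exponential event times, uniform progression times, and a clinical diagnosis rate chosen to approach 139 control diagnoses (121 to 136 were obtained). Frailty is a gamma variable that raises both event risk and the rate of clinical diagnosis.

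| Control patients diagnosed by their event | Frailty variance | Median HR | Rejection, 1000 patients |
|---|---|---|---|
| Kept | 0 | 0.36 | 100% |
| Kept | 1 | 0.34 | 100% |
| Kept | 2 | 0.33 | 100% |
| Dropped | 0 | 1.02 | 5.7% |
| Dropped | 1 | 0.70 | 30% |
| Dropped | 2 | 0.57 | 62% |

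With 700 patients and variance 0 or 1, keeping these records still gave rejection above 99%. Dropping them with variance 0 gave 4.7%. In the frailty-free setting at 1000 patients, dropping cut control events from about 56 to about 15. On section 18.1's own bookkeeping it would leave 52 − 46 = 6.

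**The case against.** Several points on the other side are fair.

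- **The false benefit is conditional.** A reader might infer that this endpoint must show a benefit whatever is done. The simulation does not support that: with time-zero records dropped and diagnosis unrelated to risk, the test holds its level. Section 19.2.2 does not fix how these records are handled, and a SAP commonly would. But 52/139 counts them, and the protocol nowhere assumes that clinical diagnosis is unrelated to risk.
- **The >99% is not a miscalculation.** It follows from its inputs and includes an assumed real 40% reduction. It also belongs to the 1000-patient plan; the revised power statements in section 18.1 concern process outcomes and the long-term primary endpoint and do not repeat it. This limits its weight but does not make the comparison valid.
- **ELF-arm patients are not shown to be low-risk.** It is tempting to say that ELF fills its denominator with milder cases. Section 18.1 assumes the same groups at the same event rate in both arms. On its figures, the control denominator is depleted of undiagnosed event-free patients.
- **The 77% does not carry over to 700 patients.** The revised assumptions are 50% v under 10% diagnosed by July 2014, or about 175 v under 35 of 350 per arm. That is a more unequal comparison, not a scaled copy of 216 v 139.
- **Varices and HCC.** One might infer the same bias towards ELF. The origin is equally invalid, but these events are detections, earlier detection may be the aim, and neither size nor direction has been shown.

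**Conclusion.** The concern holds in conditional form. The endpoint compares subsets formed after randomisation, by arm-specific rules and from arm-specific origins. Its hazard ratio and p-value are therefore not a valid randomised comparison and can favour ELF when ELF prevents nothing.

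On section 18.1's counts the size under no effect is a risk ratio of 0.64, p = 0.007 and about 77% false rejection. This rests only on the protocol's denominators and equal events per arm. In a Cox analysis a false benefit is near certain if control patients diagnosed by their complication are kept. If they are dropped, false rejection ran from about 5% to 62% at 1000 patients, depending on an assumed link between risk and clinical diagnosis. The frailty values are illustrative and are not protocol figures. The rise in power from about 67–70% to >99% comes from the unequal denominators.

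A reader might extend the criticism to the trial's main result. The documents do not support that: the primary endpoint runs from randomisation in all randomised patients.

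**What to change.** 1. In sections 17.2 and 19.2.2, report every endpoint timed from diagnosis of cirrhosis descriptively by arm, without a between-arm test or hazard ratio. State the number of control patients whose diagnosis was made by the complication.
2. Make the comparative secondary analysis time from randomisation to first severe complication in patients with baseline ELF ≥9.5. This is measured before randomisation in both arms, 9.5 is a cut point of a minimisation factor (section 12.2), and the group carries 46.4 of 51.5 expected control events (90%; the 51.5 is 46.4 + 5.1 in section 18.1).
3. If time from randomisation to varices or treatable HCC is compared, present it as a comparison of detection policies. OGD and ultrasound are not required before diagnosis (Table 4) and are scheduled only after it (sections 13.1.1, 13.1.3 and 14.3.1), so a shorter time in the ELF arm would partly reflect more looking.
4. Delete the >99% power sentence in section 18.1.

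The cost is wording in three sections and no new data. The downside is the loss of an apparently very well-powered secondary claim.

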12.2 RANDOMISATION

**PLEASE NOTE THAT THE RANDOMISATION LINE IS DUE TO CLOSE
30/04/2013.**

**RANDOMISATIONS MUST BE PERFORMED BY THIS DATE. IF THIS IS
NOT POSSIBLE, PLEASE DISCUSS SPECIFIC CASES WITH CTRU.**

Following receipt of the results of the registration ELF test, patients who fulfil the eligibility criteria for randomisation (section 7.2) will be randomised on a 1:1 basis to 'screening for cirrhosis with ELF' or 'screening for cirrhosis with standard care'. Patients who are above the threshold for randomisation should be seen following receipt of the results of the registration blood tests (including ELF testing) as soon as possible and preferably within 6 weeks of the registration visit, but up to 12 weeks is permissible. However, if there is likely to be a delay in excess of 6 weeks please contact the CTRU to discuss.

Patients should also be asked to arrive fasted for this visit to allow for Glucose \pm HOMA-IR testing. For trial purposes, a patient is considered fasted if they have gone without food either overnight or for more than 4 hours. During this fasted period, however, the consumption of water is allowed.

A computer-generated minimisation program that incorporates a random element will be used to ensure treatment groups are well-balanced for the following characteristics (details of these stratification factors will be required for randomisation):

- Centre
- Age (≥ 18 to < 40 , ≥ 40 to < 65 and ≥ 65 to < 75)
- Gender (Male, Female)
- Baseline ELF score:
(≥ 8.4 to < 9.5 , ≥ 9.5 to < 11.5 ≥ 11.5 to < 12.5 and ≥ 12.5)
- History of high alcohol consumption (at any time), defined as > 6 units*/day for 12 months or more for males and > 4 units/day for 12 months or more for females (Yes, No)
- Current alcohol consumption per day (Males: 0 units (teetotal), < 3 units (light), 3-6 units (moderate), > 6 units (high); Females: 0 (teetotal), < 2 units (light), 2-4 units (moderate), > 4 units (high))
- Type of CLD (ALD, Viral, Unknown/Other, NAFLD)

*one unit is defined as 10 grams of alcohol

Randomisation will be performed centrally using the CTRU automated 24 hour telephone registration system. Authorisation codes and PINs, provided by the CTRU, will be required to access the registration system.

The following information will be required at randomisation:

- Unique authorisation and PIN code
- Name of person randomising patient
- Patient trial number (from registration)
- Confirmation of continued eligibility
- Patient's date of birth

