12.3 SCREENING FOR CIRRHOSIS WITH ELF

Subjects in the intervention arm will have their ELF score measured every 6 months. If the ELF score is ≥ 9.5 the patient will be deemed to have cirrhosis. These patients should be contacted as soon as possible and recalled in to clinic to commence cirrhosis management. (Please see section 13)

Patients in the ELF arm will also be screened for cirrhosis using standard clinical means. If the patient is deemed to be cirrhotic on clinical criteria (by examination, on the basis of laboratory tests (other than ELF) or through imaging), the patient will have been deemed to have cirrhosis and cirrhosis management will commence.

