Power calculations are based on our hepatology estimates of the identification of large varices in cirrhotic patients and the expected identification of cirrhotic patients in the ELF and control arms. Once identified as cirrhotic, approximately 10% of patients are predicted to be treated with beta-blockers/band ligation (BB/BL) of varices.

In the ELF arm, current estimates suggest 40% of patients will be diagnosed with cirrhosis initially, and 10% diagnosed during follow up to July 2014. Therefore in this total of 50% of patients, we would predict the use of BB/BL in 1 in 10, i.e. 5% of the total. In the control arm, conservatively we predict the clinical diagnosis of cirrhosis to be made in under 10% of the patients by July 2014: therefore 1% of the total would receive BB/BL. Based on the

assumption of 700 patients randomised at the end of the recruitment period and follow up until July 2014, power is 86%. We will have approximately 40% power for this endpoint at the interim analysis in summer 2013. Similarly with the additional follow up until July 2014, we will have good power to show changes in the frequency of endoscopy and ultrasound/AFP's to detect HCC at a surgically curable stage and also to detect changes in Liver Function Tests (LFT's) in patients with Hepatitis B and Hepatitis C. The power to detect changes in the frequency of endoscopy and ultrasound/AFP's should be very good (>90%) at the interim analysis in summer 2013, and the power to detect changes in LFTs should be of the order of 60% for Hepatitis B patients and 90% for Hepatitis C patients.

As previously mentioned we will also have enough patients to have good statistical power (approximately 80%) after five years further follow up for the detection of changes in the primary endpoints of the existing trial which are major liver events and survival. These endpoints will only be delivered with long follow up of five years. This will capture major liver events and long term consequences of ELF testing, survival and health economics.

The detailed information collected within the Programme and the impact of ELF on the process of care will provide detailed information that will be essential in the interpretation of the long follow up and the impact of ELF testing on major liver events and survival.

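### Time to cirrhosis diagnosis: section 19.2.2 leaves out clinical diagnoses in the ELF arm, and one Cox hazard ratio cannot summarise an endpoint with 80–86% of that arm's expected events at time zero

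*Protocol*

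**What the plan says.** - **Endpoint.** Protocol section 17.2 lists "Time from randomisation to diagnosis of cirrhosis by ELF or clinical means", with no restriction by arm.
- **Conduct.** Section 12.3 adds that "Patients in the ELF arm will also be screened for cirrhosis using standard clinical means". A patient found cirrhotic that way is deemed to have cirrhosis and starts management.
- **Analysis definition.** Section 19.2.2 dates the endpoint to a diagnosis "either by, in the ELF arm, having an ELF score ≥ 9.5 or in the control arm, via standard methods". Section 19.2.1 carries almost the same wording.
- **Model.** In the same paragraph of 19.2.2, "Cox regression analysis, adjusting for the minimisation factors (see section 12.2), will be used to compare the differences between the survival curves". Kaplan-Meier curves and hazard ratios with 95% intervals are to be presented. Baseline ELF is a minimisation factor (section 12.2), with categories that begin "≥ 8.4 to < 9.5 , ≥ 9.5 to < 11.5".
- **Release of the result.** Under sections 6.2, 10.1.2 and 12.2, the site learns at allocation whether an ELF-arm patient's registration score is 9.5 or more, so that management can begin.
- **Forecasts (section 18.1).** At the original size, 185 of 500 patients per arm have ELF above 9.49, and total diagnoses are 216 (ELF) and 139 (control). In the revised plan for about 700 patients, "current estimates suggest 40% of patients will be diagnosed with cirrhosis initially" in the ELF arm, with a further 10% during follow-up. Under 10% of control patients are expected to be diagnosed by July 2014.

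**The concern.** There are two separate problems.

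First, the analysis rule does not match the endpoint. An ELF-arm patient diagnosed clinically while ELF is below 9.5 would be censored, or counted only when ELF later crosses the threshold. That works against the ELF arm on the trial's first aim, earlier detection.

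Second, the design puts a large block of ELF-arm events at the moment of randomisation and essentially none in control. A Cox model assumes one constant ratio of hazards over time. Here the ratio is unbounded at day 0 and something quite different afterwards. The reported figure would then reflect when the data were cut and how the software treats ties and zero times, rather than the effect of ELF screening.

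**Working it through.** **1. Reproduce the plan's counts (section 18.1, original size).**
- ELF arm: 185 + 0.10 × 315 = 216.5 (stated 216).
- Control arm: 46 + 185/3 + 0.10 × 315 = 139.2 (stated 139). The 46 reproduces as 46.4 under the stated exponential method.
- The 185 rests on the stated 37%. The quoted 80/225 is 35.6%, a small difference that does not matter here.

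**2. Share of ELF-arm diagnoses at time zero.**
- Of patients: 185/500 = 37%, or 40% in the revised forecast.
- Of diagnoses: 185/216 = 86%, or 40/(40 + 10) = 80%.
- Control: essentially none, because section 6.2 bars randomisation of anyone judged cirrhotic at that visit and control ELF scores are not released.

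**3. What the planned adjustment does (original counts).**
- Baseline ELF ≥ 9.5: every ELF-arm patient has the event at time zero, while control diagnoses (46 + 62 = 108 of 185) come later. The partial likelihood within this group rises without limit as the hazard ratio grows, so there is no finite estimate.
- Baseline ELF 8.4–9.49: 10% are diagnosed in each arm, so the hazard ratio is about 1.
- The single adjusted hazard ratio is a blend of these two.

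**4. Size.** Large simulated samples were built from the original counts. Assumptions: exponential times; diagnosis recorded at 6-monthly visits; counts reached at 42 months (mean of 24 months' accrual plus 30 months' follow-up, 12 + 30); time-zero events kept at a small positive time; the only covariate is baseline ELF split at 9.5. Hazard ratios, ELF against control:

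| Follow-up (months) | Kept, unadjusted (Efron) | Kept, adjusted (Efron) | Kept, adjusted (Breslow) | Dropped, adjusted |
|---|---|---|---|---|
| 6 | 9.2 | 298 | 56 | 0.92 |
| 12 | 5.1 | 116 | 27 | 0.93 |
| 30 | 2.6 | 37 | 11 | 0.99 |
| 60 | 1.7 | 16 | 6.4 | 0.99 |
| 93 | 1.5 | 9.9 | 4.7 | 0.99 |

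Repeat simulations gave 8.4–9.2 unadjusted at 6 months and 2.5–2.6 at 30. Adjusted (Efron), they gave about 240–300 at 6 months and 34–44 at 30. At 30 months the choice of tie method alone moves the planned estimate about threefold (37/11 = 3.4).

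**5. Revised forecast.** This uses 350 per arm and assumes the control diagnoses split 28 and 7 by baseline ELF, since the protocol gives no split. With time-zero events kept, the unadjusted hazard ratio is 19 at 6 months and 5.9 at 30. Adjusted, it is 865 and 155 (Efron) or 150 and 41 (Breslow). The instability remains.

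**6. The same original-count data as cumulative incidence.**
- Day 0: 185/500 against 0, a difference of 37 points.
- 6 months: 189/500 − 26/500 = 37.8% − 5.2% = 32.6 points.
- 30 months: 208/500 − 108/500 = 41.6% − 21.6% = 20.0 points.

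Each of these is a defined quantity that does not depend on tie handling.

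**The case against.** The best defence has four parts. This is a secondary endpoint. The planned Kaplan-Meier curves would show the day-0 drop to any reader. Handling of time-zero records is properly left to the SAP, which is not shown. The wording in 19.2.2 may be shorthand for what distinguishes the arms, since 12.3 and 17.2 define clinical diagnoses in the ELF arm and the cirrhosis form collects them. The first two points lower the severity. The third is fair as far as it goes, but no coding rule makes these hazards proportional, and the protocol itself fixes the hazard ratio. The fourth means that the wording can be repaired without loss of data; the texts still conflict.

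Three stronger readings are tempting, and the documents do not support them.
- **The hazard ratio could reverse.** A value near 0.3 (0.24–0.38) appears only if time-zero records are dropped, baseline ELF is left unadjusted and the original counts are used. The plan does adjust for baseline ELF, and the result is then about 1. Under the revised forecast, dropping records gives 1.7–2.0 unadjusted and roughly 5–6 adjusted. With records kept, the ratio never falls below 1 at any follow-up length examined.
- **The hazards cross.** After day 0 the original counts give 31/315 = 10% in the ELF arm against 139/500 = 28% in control. The revised forecast gives 10/60 = 17% against under 10%, so there is no crossing on current figures.
- **Times could be negative.** The dating rule that mentions a blood sample ("in clinic, date of clinic visit or blood sample") belongs to the preceding endpoint, severe complications after diagnosis. The time-to-diagnosis paragraph uses the in-clinic date, and the site first learns of a score of 9.5 or more at randomisation. That gives time zero.

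**Conclusion.** The point stands in two parts. Section 19.2.2, read literally, contradicts sections 12.3 and 17.2 on what counts as a diagnosis in the ELF arm. How many diagnoses this affects cannot be estimated, because the protocol gives no forecast of clinical-only diagnoses in that arm. Separately, with 37–40% of ELF-arm patients and 80–86% of that arm's expected diagnoses at randomisation, the planned hazard ratio is not a stable quantity. On the protocol's own forecasts the adjusted estimate at 30 months can be about 35–45, 11–13 or 1, depending on tie method and on whether time-zero records are kept. The exact values rest on the simulation assumptions above. The lack of proportionality does not: it follows from releasing the ELF result at allocation. The point should be fixed; it does not touch the primary comparison, which runs from randomisation to first severe complication.

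**What to change.** - In sections 19.2.1 and 19.2.2, count an ELF-arm diagnosis as ELF ≥ 9.5 or clinical, whichever comes first. Date it from the in-clinic notification and no earlier than randomisation.
- For time to diagnosis, replace the single Cox hazard ratio with between-arm differences in cumulative incidence, with 95% intervals, at fixed times from randomisation: for example day 0 and 6, 12, 18, 24 and 30 months, with death as a competing event. If one number is wanted, use the difference in restricted mean time to a fixed horizon.
- Section 19.2 has all analyses "carried out at a 2-sided 5% level of significance", so name in advance the one time point, or the restricted mean, that carries the test.
- Show ELF-only and clinical diagnoses separately, so that the day-0 block is visible as ELF-only.

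The cost is a change of wording in the protocol and SAP, with no new data. The downside is several time points in place of one hazard ratio. Estimates at the later times will also rest on fewer patients in July 2014, because those randomised at the end of April 2013 will have only about 15 months of follow-up by then.
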